## List of Abbreviations

AE	Adverse Event/Adverse Experience
CFR	Code of Federal Regulations
CRF	Case Report Form
CSOC	Clinical Study Oversight Committee
DCC	Data Coordinating Center
DHHS	Department of Health and Human Services
DSMB	Data and Safety Monitoring Board
FFR	Federal Financial Report
FWA	Federal Wide Assurance
GCP	Good Clinical Practice
HIPAA	Health Insurance Portability and Accountability Act
ICF	Informed Consent Form
ICH	International Conference on Harmonization
IRB	Institutional Review Board
ISM	Independent Safety Monitor
MOP	Manual of Procedures
n	Number (typically refers to participants)
NIH	National Institutes of Health
OHRP	Office for Human Research Protections
OHSR	Office of Human Subjects Research
PI	Principal Investigator
QA	Quality Assurance
QC	Quality Control
SAE	Serious Adverse Event/Serious Adverse Experience
SOP	Standard Operating Procedure
US	United States
CBD	Cannabidiol
THC	Tetrahydrocannabinol
AUD	Alcohol Use Disorder

# **Protocol Summary**

Title	A Phase I/II Randomized, Double-Blind, Placebo-Controlled Trial of Cannabidiol for Alcohol Use Disorder comorbid with Post Traumatic Stress Disorder
Brief Summary	The proposed study is a double-blind, randomized proof-of-concept study designed to assess feasibility and contrast effects of CBD treatment to those of placebo on safety, drinking-related outcomes and PTSD related outcomes in patients with AUD+PTSD. We will evaluate the safety of an extended daily CBD treatment regimen in an AUD+PTSD population, measure resulting CBD, THC, and anandamide levels, and generate preliminary data on the impact of CBD on alcohol use, PTSD symptoms, and neuropsychological and neurophysiological domains implicated in AUD and PTSD. 150 participants will be enrolled to randomize 48 eligible participants who fully meet study criteria in a 5:3 ratio to receive either 600mg CBD/day (PO) or placebo respectively for 6 weeks (N=30 participants on CBD and N=18 participants on placebo). Clinical interviews or portions of the interview will be audio taped to ensure quality control. Deidentified audio recordings of participants who consent to participate in the voice-markers analysis will be encrypted and sent via secure sites for analysis to a HIPAA compliant specialized labs.
Phase	Clinical study phase I/II
Objectives	To assess the safety and feasibility of administering CBD in an AUD+PTSD population; to generate preliminary data on the effect of CBD in reducing self-reported measures of alcohol use and PTSD symptoms and the impact of CBD upon neurophysiological and neuropsychological domains relevant to AUD+PTSD; to assess plasma for CBD, THC and anandamide levels.
Methodology	Double-blind, placebo-controlled
Endpoint	Primary endpoints: Adverse events and scores on psychomotor and cognitive tasks, number of drinks per day and PCL-5 total score. Secondary endpoints: circulating concentrations of CBD, THC and anandamide.
Study Duration	2 years
Participant Duration	9 weeks
Duration of IP administration	6 weeks
Population	n=48 (randomized) 18–70 year-old males and females with moderate to severe AUD, as well as a DSM diagnosis of either PTSD or subthreshold PTSD in the New York area.
Study Sites	New York University Grossman School of Medicine
Number of participants	150 participants expected to be enrolled, 48 participants expected to be randomized
Description of Study Agent/Procedure	Cannabidiol PO 600mg/day
Reference Therapy	Placebo with medication management
Key Procedures	Blood draws

	The primary outcome measure for AUD, the number of drinks per day, is the change from baseline to treatment end (week 6, T8), as analyzed with a Mixed Model Repeated Measures (MMRM) with within and between group comparisons. The primary outcome measure for PTSD, PCL-5 total score, and secondary outcomes for traumatic stress induced craving from the human laboratory task, and AUD and PTSD related domains will be analyzed in the same manner.
Statistical Analysis	For secondary outcomes of plasma levels within- and between-group comparisons of plasma CBD levels will be assessed at baseline (pre-CBD levels), following 45 minutes (T1- 45min post-CBD levels), 1 day (T2- 45min post-CBD levels), 1 week (T3- 45min post-CBD and pre-CBD levels), 2 weeks (T4- 45min post-CBD and pre-CBD levels), 4 weeks (T6- 45min post-CBD and pre-CBD levels), 6 weeks (T8- 45min post-CBD and pre-CBD levels), and 7 weeks (T9- pre-CBD levels) after the first CBD vs. placebo dose. Effects of dose will be assessed and the interaction between group and time-points will be evaluated.

# 2 Introduction, Background Information and Scientific Rationale

# 2.1 Background Information and Relevant Literature

# Need for improved treatments for AUD comorbid with PTSD

Alcohol use disorder (AUD) is one of the most common and debilitating psychiatric disorders. It has a lifetime prevalence of ~29.1% in the United States, and is a major cause of medical and social disability, preventable death and economic burden (\$249 billion in 2010) [1, 2]. Several medications are available for treating AUD, however associated effect sizes treatment compliance rates remain low [3] [4, 5]. A major barrier to improving medical treatment of AUD is the high level of heterogeneity between individuals with this disorder: AUD comprises multiple clinical subtypes with distinct patterns of alcohol misuse and distinct psychological and neurobiological disturbances. This means that a given medication may only work for certain subtypes of AUD patients, leading to overall lower treatment effectiveness in the absence of more targeted approaches. Differing co-existing psychiatric disorders (present in a high proportion of individuals with AUD) make an important contribution to this heterogeneity in [6-8]. The National institute of Alcohol use disorder (NIAAA) has therefore emphasized ongoing drug development should address this heterogeneity by targeting potential treatments to specific AUD subpopulations including psychiatric comorbidities, particularly those that are common, that involve severe AUD, and have low treatment response [6-8].

Based on these criteria, the NIAAA recently mandated research to target medications to AUD comorbid with post-traumatic stress disorder (PTSD) [6-8]. PTSD is a condition that may develop following a traumatic event: it involves intrusive thoughts about the traumatic event, avoidance of event relevant stimuli, negative changes

#### #S17-00949

in mood and cognition, heightened vigilance and physiological arousal. PTSD is present in 30-60% of individuals diagnosed with AUD and conversely 20–70% of individuals diagnosed with PTSD meet criteria for AUD, with higher rates in military veterans; there this comorbidity (AUD+PTSD) represents a significant proportion of all AUD [9-14]. Subthreshold PTSD criteria requires that at least six symptoms of PTSD are present, but do not meet full threshold criteria due to failure to meet criterion specifiers. Previous research has shown that subthreshold PTSD is a clinically relevant concept. For instance, it has been found that psychiatric outpatients with subthreshold PTSD had social and occupation morbidity levels comparable to those with fully-threshold PTSD [104]. Other research has also found high rates of psychiatric comorbidity and psychosocial impairment in a sizable epidemiologic study [105]. Similar outcomes have been shown in samples of veterans [103]. When examining the leading subthreshold definitions utilized by clinicians the Six-symptom definition was found to trend toward significance and perform the best of all four definitions tested [102]. In addition, AUD+PTSD/subthreshold PTSD is associated with more severe AUD, higher mortality and impairment and poorer response to treatment. Findings also suggest that this comorbidity involves a vicious cycle in which each disorder exacerbates and impedes treatment of the other [10, 12, 15-22]; therefore, coordinated treatment of both disorders should be more efficacious than treating each disorder in isolation. Various medications have been tested for AUD or efficacy in randomized clinical trials involving AUD+PTSD/subthreshold PTSD patients. However, no Phase III trials have been reported [23].

### Stress induced craving and extended amygdala activation as a target for treating AUD+PTSD

Perhaps the most promising medication target for treating AUD+PTSD/subthreshold PTSD is the addiction domain of stress-induced alcohol craving, with the neurobiological substrate of increased activity in the extended amygdala. Clinical studies find that AUD+PTSD/subthreshold PTSD patients use alcohol as a coping mechanism to reduce stress associated with PTSD/subthreshold PTSD [10, 12, 15-22, 24-26]. Animal models show stress and alcohol craving are linked by common neurobiological circuits, namely the extended amygdala, and that pharmacological inhibition of stress or ethanol-withdrawal associated activity in this area simultaneously reduces both anxiety and ethanol-seeking behaviors [27-29]. Receptor actions implicated in this inhibitory effect include cannabindoid 1 (CB1) receptor stimulation and 5-HT1a receptor activation [27-29]. Clinical and human experimental studies support the idea that increased stress and amygdala activation increases alcohol craving and use. In AUD patients who report alcohol use to mitigate negative emotions, higher amygdala reactivity predicts future problem drinking [30]. In PTSD/subthreshold PTSD patients, PTSD symptoms predict alcohol craving and use [16, 31]; further, a hyper-reactive amygdala response to threat, and heightened sympathetic physiological arousal including skin conductance and heart rate, reliably distinguishes PTSD/subthreshold PTSD from controls and predicts PTSD symptoms [2, 32-34]. The well-validated human laboratory paradigm of guided trauma imagery-elicited alcohol craving shows that trauma re-experiencing elicits negative emotion, physiological arousal, and alcohol craving [35-39].

Potential for CBD to treat AUD+PTSD/subthreshold PTSD by targeting stress induced extended amygdala activation Cannabidiol (CBD), a pharmacologically broad spectrum anxiolytic and nonpsychotomimetic phytocannabinoid contained in cannabis, is a promising drug candidate for reducing negative emotion-induced alcohol craving. In animal models, CBD produces anxiolytic, anti-compulsive, anti-fearconditioning and pro-fear-extinction effects, by acting at serotonin 1A (5-HT1a) and CB1 receptors within extended amygdala areas (the central nucleus [40], bed nucleus of the stria terminalis [41-43] and nucleus accumbens shell [44]), and within functionally connected brain regions including the periagueductal grey [45], prelimbic and infralimbic regions of the medial prefrontal cortex [46], and hippocampus [47], reviewed in [48]. CBD indirectly increases endocannabinoid agonism at the CB1 receptor [49], an action that reduces extended amygdala output and alcohol seeking [50]. CBD also potently reduced ethanol seeking in animal models of relapse during 7-days of treatment, and drug seeking remained fully attenuated up to 5 months following treatment termination [51]. In human experimental studies, CBD at doses between 300-800 mg rapidly (within 2 hours) reduces subjective anxiety in both healthy and social anxiety disorder subjects, and reduces threat related amygdala activity and sympathetic arousal measured by skin conductance [52], reviewed in [48]. Importantly, skin conductance and amygdala activation were reduced by CBD in a closely correlated manner [53], suggesting threat related sympathetic arousalmay serve as a proxy for amygdala activation [52]. These findings suggest that CBD will reduce extended amygdala activity and negative emotion associated with PTSD symptoms, and thereby, reduce alcohol craving and use. Further findings suggest that human laboratory measures of the subject and physiological effects of traumatic stress upon emotional state and alcohol craving may serve as a useful measure of drug target engagement.

# a. Name and Description of the Investigational Agent

#### #S17-00949

Cannabidiol (CBD) is a phytocannabinoid constituent of cannabis that lacks the psychotomimetic and rewarding effects of tetrahydrocannabinol (THC) [54], and has an excellent safety profile in the human experimental studies and clinical trials reported thus far [43, 55]. CBD is a schedule 1 drug, a class that includes compounds with high potential for abuse and no medical value. Contrary to this scheduling, CBD does not appear to possess a high abuse potential. Nonetheless, this formulation has not been FDA-approved for medical use. Therefore, this study will be performed under an Investigational New Drug Application (140108).

CBD has a broad spectrum of pharmacological effects. As distinct from THC, CBD is a very low-affinity cannabinoid 1 (CB1) receptor ligand; nevertheless CBD appears to achieve an agonist effect at this receptor, potentially by inhibiting fatty acid amide hydroxylase (FAAH), which is the enzyme responsible for hydrolysis the endocannabinoid anandamide, which acts as CB1 agonist [49]. In addition to its impact on the endocannabinoid system, CBD also acts as an agonist at the serotonin 1A (5-HT1A) receptor [42, 56]; produces allosteric modulation of ligand-binding kinetics at  $\mu$  and  $\delta$  opioid receptors [57]; increases intracellular calcium through activation of transient receptor potential vanilloid type 1 (TRPV1) cation channels [58]; enhances adenosinergic neurotransmission via inhibition of the adenosine transporter [59]; CBD also regulates, directly or indirectly, the peroxisome proliferator-activated receptor- $\gamma$ , the orphan G-protein-coupled receptor 55, the equilibrative nucleoside transporter, additional TRP channels, glycine receptors and GABA receptors [11, 12, 19, 21]. CBD may also have non-receptor based enzymatic and other effects. Only some of these actions (CB1 and 5-HT1A actions) have been related to animal model effects of CBD anxiolytic or anti-addictive effects [48].

#### 2.2.1 Preclinical Data

As discussed, extensive evidence in animal models shows that CBD reduces anxiety behaviors, compulsive behaviors, panic response and physiological stress responses by inhibiting extended amygdala activation and promoting response in the hippocampus and medial prefrontal cortex [48]. This suggests the potential to reduce stress-induced craving. Several other effects of CBD may also act improve PTSD symptoms and combat alcohol addiction. Cannabidiol modifies consolidation and reconsolidation, suggesting the ability to modify traumatic memories [48, 60]; CBD produces several pro-cognitive effects: including protecting against ethanol induced neurotoxicity [61], promoting hippocampal neurogenesis [47], and attenuating cognitive impairment in several animal models of neurodegenerative disease [62] [63].

Animal model studies also show that CBD reduces addictive behaviors: CBD reduces cue-induced heroin seeking, potentiates extinction of cocaine- and amphetamine-induced conditioned place preference [64], and normalizes heroin-seeking-induced changes in glutamatergic GluR1-containing amino-hydroxy- methyl-isoxazolepropionic (AMPA) receptors and CB1 receptor expression in the nucleus accumbens [65] induced by alcohol intoxication in a delay discounting task 6-15 days after the cessation of treatment.

#### 2.2.2 Clinical Data to Date

Clinical trials in PTSD or anxiety: No clinical trials of CBD for PTSD/subthreshold PTSD have been reported, nor for any anxiety related outcome – although some trials in anxiety may be currently in progress. In human experimental studies, CBD at doses between 300–800 mg rapidly (within 2 hours) reduces subjective anxiety in both healthy and social anxiety disorder subjects, and CBD reduces threat-related amygdala activity and sympathetic arousal measured by skin conductance [66] [43, 48, 52].

Clinical trials in AUD: No extended clinical trials of CBD's effects in alcohol use disorder or any addictive disorder have yet been reported. However, there are limited studies of CBD's acute effects on addiction- related behaviors. The only study to assess the impact of CBD on alcohol-related behaviors found no impact of 200mg of CBD on symptoms of intoxication in healthy volunteers [67]. CBD was also reported to reduce cigarette smoking in dependent humans [68], and a single case study reported that daily CBD prevented marijuana withdrawal symptoms [69].

Other clinical data: A considerable and rapidly growing number of human experimental studies and clinical trials of CBD's effects in other neuropsychiatric disorders (other than PTSD/subthreshold PTSD or AUD) have been conducted. Findings in general show CBD to have multiple therapeutic effects, including anxiolytic, anti-addictive, anticonvulsive, antipsychotic and analgesic [70], combined with an excellent safety profile and lack of adverse effects [43, 55]. GW pharmaceuticals is developing CBD (Epidiolex®) as a medication for the treatment of seizures associated with Lennox-Gastaut syndrome and Dravet syndrome, and recently completed successful Phase 3 trials in 2016 [71, 72], and a successful Phase 2 trial in schizophrenia [73].

# 2.3 Rationale

There is an urgent need for medications that are effective in treating AUD+PTSD/subthreshold PTSD comorbidity, and which are targeted to specific addiction domains and their neurobiological substrates. Preclinical and human experimental findings suggest the phytocannabinoid CBD is a promising candidate medication for reducing stress induced craving by inhibiting extended amygdala output, in addition to potential anti-addictive, traumatic and addictive memory modifying and pro-cognitive effects, thereby providing an integrated treatment for both AUD and PTSD/subthreshold PTSD. This promise is augmented by CBD's proven safety record, lack of intoxicating effects and low potential for abuse. Clinical trials of CBD in other disorders together with human experimental studies provide a strong basis for determining a suitable therapeutic dose for AUD+PTSD/subthreshold PTSD. There are few or no clinical trials reported of CBD for AUD, PTSD/subthreshold PTSD, or more generally for stress and addiction disorders, creating a mandate for the current trial.

The proposed study is a double-blind, randomized proof-of-concept study designed to assess feasibility and contrast effects of CBD treatment to those of placebo on safety, drinking-related outcomes and PTSD/subthreshold PTSD related outcomes in patients with AUD+PTSD/subthreshold PTSD. We will evaluate the safety of an extended daily CBD treatment regimen in an AUD+PTSD/subthreshold PTSD population and measure resulting CBD, THC, and anandamide levels. We will also generate preliminary data on the impact of CBD on alcohol use, PTSD symptoms, a human laboratory traumatic stress induced craving task, neuropsychological and neurophysiological domains implicated in AUD and PTSD/subthreshold PTSD, and cognitive ability. Cannabidiol levels will be obtained from CBD-treated participants to estimate the plasma levels corresponding with putative therapeutic effects and to determine whether dose accumulation occurs. THC levels will be obtained from CBD-treated participants to determine whether CBD metabolites are converted into THC, as has been suggested in the literature [77]. Anandamide levels will be obtained from all participants to test whether CBD elevates plasma anandamide, and to provide preliminary data for relating anandamide levels to putative therapeutic effects. Following screening and baseline assessments, 48 participants will be randomized in a 5:3 ratio to receive either 600mg CBD/day (PO) or placebo respectively for 6 weeks (N=30 participants on CBD and N=18 participants on placebo). Safety measures (adverse events, cognitive and motoric function), drinking related outcomes and PTSD symptoms will be assessed weekly throughout the study. Human laboratory tasks, neuropsychological domains implicated in AUD and PTSD/subthreshold PTSD and cognition will be assessed at baseline and at the end of treatment. Measurement of circulating levels of Delta-9 THC, 11-Hydroxy Delta-9 THC and Delta-9 Carboxy THC will be obtained from CBD-treated participants only at baseline, 45 minutes, 1 day, 1 week, 2 weeks, 4 weeks, 6 weeks, and 7 weeks after treatment with the first dose of CBD vs. placebo. Anandamide levels will be obtained from both CBD- and placebo-treated participants at the aforementioned timepoints.

## Version: 4.3 2.4 Potential Risks & Benefits

#### 2.3.1 Known Potential Risks

The available evidence suggests that CBD is safe and well-tolerated in human participants. Numerous studies, including several blinded, placebo-controlled trials, have revealed few adverse effects of CBD orally in doses ranging from 10 mg to 1500 mg per day; there have been no reported effects on blood pressure, heart rate, or respiratory rate, no negative mood effects, and no psychomotor slowing. Commonly reported treatment-emergent adverse events in Phase 3 trials of CBD for Lennox-Gastaut or Dravet Syndrome included diarrhea, somnolence, pyrexia, decreased appetite, vomiting, fatigue, lethargy, convulsion, and elevated liver enzymes. All participants in these trials were on concomitant anti-seizure medications. CBD is not noticeably psychoactive.

#### 2.3.2 Incidental Findings

In some cases, the safety blood draw results may indicate an abnormality with (or without) a clinical significance. Every blood draw performed in this study will be saved and handled under the standard PHI confidentiality restrictions and regulations employed for patients' information. The results are always reviewed by a licensed nurse practitioner or an MD, who may then detect an abnormality. If clinically useful information is uncovered, either the Principal Investigator or another clinician on the study will speak to the participant in person or on the telephone regarding the new information. A copy of the original report will also be provided to the participant who will then be advised to consult with their treating physician.

#### 2.3.3 Known Potential Benefits

Participants may or may not experience clinical benefit from this study. Pre-existing clinical data suggest a possibility that the study drug could produce anxiolytic and anti-addictive effects. Aspects of study participation likely to be beneficial include free medical and psychiatric evaluations, and the attention and support of participating in a clinical trial.

# **3 Objectives and Purpose**

## 3.1 Primary Objective

The primary objective is to obtain a preliminary assessment of the safety, tolerability, efficacy, and effect size of CBD in reducing self-reported measures of alcohol use and PTSD symptoms in the AUD+PTSD/subthreshold PTSD population.

We predict that treatment with 600mg CBD daily will be well tolerated with no greater psychomotor or other motor side effects compared to treatment with placebo. We predict that CBD will be associated with a greater reduction in drinks per day and PTSD symptoms (total PCL-5 score) compared to placebo.

## 3.2 Secondary Objectives

Secondary objectives of this study are as follows.

- To assess the effect of CBD upon plasma CBD and THC levels when administered to patients with AUD+PTSD/subthreshold PTSD. We predict that within-group plasma CBD levels will stabilize within one week, i.e. 45 minutes post-CBD dosing levels obtained after 1 week of treatment will not differ from those obtained after 4 weeks of treatment.
- 2) To contrast the effects of CBD to those of placebo on psychological and cognitive domains relevant to AUD and PTSD/subthreshold PTSD. Relative to placebo, we predict that CBD will improve self-report measures of craving, anxiety, mood, and self-efficacy, and improve cognitive function. We will also specifically target the domain of traumatic stress induced craving using a human laboratory task. We predict that relative to placebo, CBD will lead to a greater attenuation in subjective traumatic stress and alcohol cue-induced craving and accompanying physiological stress response.
- 3) To assess the effect of CBD on plasma anandamide levels. We will contrast levels of plasma anandamide between samples taken at baseline and after CBD treatment, and between samples taken at predicted preand 45 minutes post-dosing CBD levels. We predict that relative to placebo, CBD will lead to an increase in plasma anandamide between these time points.
- 4) To assess the temporal relationship between the onset in reduction of PTSD symptoms and the onset in reduction of AUD symptoms. We predict that a reduction in PTSD symptoms will precede a reduction in

Exploratory Aim 1: To examine voicemarkers as a function of a patient's AUD and PTSD status and to develop assessment models that use lexical and prosodic features to classify a patient's AUD and PTSD status.

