#### Plasma CBD, THC and anandamide levels

Measurement of circulating levels of CBD, THC, Delta-9 THC, 11-Hydroxy Delta-9 THC and Delta-9 Carboxy THC will be obtained from CBD-treated participants at baseline (pre-CBD levels), following 45 minutes (T1-

45min post-CBD levels), 1 day (T2-45min post-CBD levels), 1 week (T3-45min post-CBD and pre-CBD levels), 2 weeks (T4-45min post-CBD and pre-CBD levels), 4 weeks (T6-45min post-CBD and pre-CBD levels), 6 weeks (T8-45min post-CBD and pre-CBD levels), and 7 weeks (T9- pre-CBD levels) after the first CBD vs. placebo dose. Anandamide levels will be obtained from both CBD- and placebo-treated participants at the aforementioned timepoints. All three levels (CBD, THC and anandamide) will be determined via High Performance Liquid Chromatography/Tandem Mass Spectrometry (LC-MS/MS) by the Nathan Kline Institute.

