#### 7.1.1 Confirmation of target CBD plasma levels and measurement of THC levels:

Circulating levels of CBD, THC and THC metabolites (Delta-9 THC, 11-Hydroxy Delta-9 THC and Delta-9 Carboxy THC) will be obtained from CBD-treated participants baseline (pre-CBD levels), following 45 minutes (T1- 45min post-CBD levels), 1 day (T2- 45min post-CBD levels), 1 week (T3- 45min post-CBD and pre-CBD levels), 2 weeks (T4- 45min post-CBD and pre-CBD levels), 4 weeks (T6- 45min post-CBD and pre-CBD levels), 6 weeks (T8- 45min post-CBD and pre-CBD levels), and 7 weeks (T9- pre-CBD levels) after the first CBD vs. placebo dose. All of these levels (CBD, THC and THC metabolites) will be determined via High Performance Liquid Chromatography/Tandem Mass Spectrometry (LC-MS/MS) at [name] Lab at the Department of Cell Biology at NYU Langone Health.

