#### 45 minutes +/- 10 minutes (T1)

- Collect blood and plasma for CBD, THC, and AEA levels at 45 minutes post medication (post-CBD levels)
- Record adverse events as reported by participant or observed by investigator
- · Results of evaluations of safety, and psychomotor effects
- Record participant's adherence to treatment program

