## 20.2 Statistical Hypotheses

Hypothesis 1a Safety and tolerability: CBD will be safe and well tolerated and will not lead to increased plasma THC. No clinically significant cognitive or motoric impairments, CBD-related serious adverse events, persisting adverse effects or treatment associated increases in plasma THC will be observed.

Hypothesis 1b: Alcohol use. Relative to the placebo-treated group, CBD-treated participants will have fewer drinks per day during the 6 weeks of treatment with CBD vs placebo.

Hypothesis 2: PTSD symptoms. Relative to the placebo-treated group, CBD-treated participants will lower PTSD symptoms during the 6 weeks of treatment with CBD vsplacebo.

Hypothesis 3a: Mechanism, traumatic stress-induced craving: Relative to placebo, CBD will be associated with a greater reduction between baseline and end of treatment in trauma induced alcohol craving, negative emotion, and psychophysiological arousal in response to the task.

Hypothesis 3b: Mechanism, AUD and PTSD related measures and cognition: Relative to placebo, CBD will improve self-report measures of craving, anxiety, mood, self-efficacy and cognitive performance.

Hypothesis 3c: Mechanism, anandamide: Relative to placebo, CBD will be associated with a greater increase

Hypothesis 4: CBD plasma levels. Within-group plasma CBD levels will stabilize within one week, i.e. 45 minutes post-CBD dosing levels obtained after 1 week of treatment will not differ from those obtained after 4 weeks of treatment at each dose.

Exploratory Hypothesis 1: Relationship between effects on PTSD symptoms and alcohol use. The onset of reduction in PTSD symptoms will precede the onset of reduction in alcohol use.

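### The only stated criterion for CBD steady state uses the 45-minute post-dose level, while the pre-dose levels already drawn at T3, T4, T6 and T8 have no criterion attached

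*Combined protocol and SAP*

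**What the plan says.** Section 2.3 gives one purpose of the CBD levels as "to determine whether dose accumulation occurs", without naming a sample. Objective 1 in section 3.2 turns this into a prediction: "45 minutes post-CBD dosing levels obtained after 1 week of treatment will not differ from those obtained after 4 weeks of treatment". Hypothesis 4 in section 20.2 opens with "Within-group plasma CBD levels will stabilize within one week" and explains it by the same 45-minute comparison.

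Pre-dose samples are scheduled alongside. Section 7.1.1 lists "1 week (T3- 45min post-CBD and pre-CBD levels), 2 weeks (T4- 45min post-CBD and pre-CBD levels") and "4 weeks (T6- 45min post-CBD and pre-CBD levels), 6 weeks (T8- 45min post-CBD and pre-CBD levels"). Section 4.2.2 has the same list, and the visit descriptions in section 7.3.3 include both draws. The Protocol Summary says "within- and between-group comparisons of plasma CBD levels will be assessed at baseline (pre-CBD levels") and goes on to list the later samples, pre-dose ones included. Section 20.3.3 analyses CBD by visit, in the same way as anandamide, and does not say which sample is meant. Section 20.3.4 tabulates means by visit, also without saying.

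Under section 6.1.5 the morning dose is two 200 mg capsules after a light meal, and the evening dose is one capsule about 12 hours later. A tolerance for the post-dose draw appears once, in the visit heading "45 minutes +/- 10 minutes (T1"). None is given for T3 or T6.

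**The concern.** Accumulation means drug carried over from one dose to the next. The pre-dose level measures that directly. The 45-minute level measures it plus whatever part of that morning's dose has been absorbed. That second part does not grow with accumulation, so it dilutes the week 4/week 1 ratio. It also varies with the meal, the speed of absorption and the exact time of the draw.

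As worded, a 45-minute comparison that shows no difference supports stabilisation within a week even if troughs are still rising. The statement bears on safety: the dose rationale in section 2 relies on there being no progressive accumulation, and section 20.4 says the trial is meant to help plan confirmatory trials.

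**Working it through.** The plan states no power, margin, half-life, absorption rate or variability for this comparison, so there is no figure to reproduce. What follows shows how far the choice of sample could matter.

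**Inputs from the documents.** 30 participants on CBD; T3 against T6 (days 7 and 28); 400 mg in the morning and 200 mg in the evening; two-sided test at 0.05.

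**Assumptions.** k = contribution of the new dose at 45 minutes divided by the week 1 trough, 0.25 to 10. Within-participant CV 30% to 60% for the trough and 30% to 60% for the new dose. Carried-over drug does not fall noticeably in 45 minutes. Paired t test on log levels.

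**Step 1, dilution.** Week 1 level at 45 minutes = 1 + k and week 4 level = R + k, in units of the week 1 trough. The ratio is (R+k)/(1+k). For R = 1.5 and k = 3 it is 4.5/4 = 1.13. The new dose's share of the week 1 reading is k/(1+k).

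**Step 2, simulated power, 30 pairs** (the range is over the CVs)

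| k | New-dose share | Ratio, R=1.5 | Power at 45 min | Ratio, R=2 | Power at 45 min |
|---|---|---|---|---|---|
| 0.25 | 20% | 1.40 | 0.75–1.00 | 1.80 | 0.99–1.00 |
| 1 | 50% | 1.25 | 0.53–0.97 | 1.50 | 0.95–1.00 |
| 3 | 75% | 1.13 | 0.21–0.53 | 1.25 | 0.55–0.97 |
| 5 | 83% | 1.08 | 0.12–0.25 | 1.17 | 0.30–0.71 |
| 10 | 91% | 1.05 | 0.06–0.09 | 1.09 | 0.12–0.27 |
| Trough | none | 1.50 | 0.78–1.00 | 2.00 | about 1.00 |

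Fewer than 30 pairs are possible: T3 and T6 include no liver function tests, and section 7.3.3 allows visits without safety labs to be remote. With 24 pairs and R = 1.5, trough power is 0.67 to 1.00, and 45-minute power at k = 3 is 0.16 to 0.43.

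**Step 3, when the loss disappears.** Under one-compartment kinetics with half-life h hours, the trough ratio is close to (1 − 2^(−672/h))/(1 − 2^(−168/h)), since 28 days is 672 h and 7 days is 168 h. At h = 60 it is 1.17; at h = 240 it is 0.856/0.384 = 2.23. Full superposition of the 400/200 mg regimen (absorption rate 0.2 to 1.0 per hour, lag 0 to 0.7 h) over h = 60 to 240 gives trough ratios of 1.17 to 2.24 and 45-minute ratios of 1.15 to about 2.2. The new dose is then at most about a tenth of the 45-minute level, and the two samples agree.

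**Step 4, two-phase kinetics** (assumed fast half-life 3 h; CV 30% in bioavailability and 40% to 70% in absorption)
- Slow half-life 4 days carrying 30% of AUC: ratio 1.23 at trough and 1.09 at 45 minutes; power 97% to 99% against 14% to 20%.
- The same with 15% of AUC: 47% to 57% against 7% to 8%. With 5% of AUC the rise is only 3% to 6%, and neither sample detects it.
- Slow half-life 4 days with a slow phase of 5% of the concentration curve: 100% against 58% to 75%.
- Slow half-life 2.5 days, slow phase 5% or 15% of the concentration curve, with 10% missed doses and 1.5 h timing error: 52% to 82% against 16% to 56%.

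**Step 5, precision of a trough comparison.** For CV 30% the SD of one log level is √ln(1.09) = 0.294, and of the log ratio 0.294 × √2 = 0.415. The 95% half-width with 30 pairs is 2.045 × 0.415/√30 = 0.155, a factor of 1.17. For CV 60% the SD of the log ratio is √ln(1.36) × √2 = 0.784 and the half-width 0.293, a factor of 1.34. For a true 25% rise the trough test itself has power of only 0.32 to 0.83, so non-significance does not show stability with either sample.

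**The case against.** The troughs are not discarded. The Protocol Summary lists them among the levels to be compared, and section 7.2.1 says blood is drawn to establish both pre-dose and post-dose levels. A reader might infer that the trial ignores its pre-dose samples, and that would be wrong. Objective 1 is a prediction with no go/no-go rule, in a pilot whose stated focus is characterisation (section 20.3.1), and a formal SAP is still to come (section 20.1). The dose rationale also cites two repeated-dose studies without progressive accumulation.

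The trough has weaknesses too. The preceding evening capsule is taken at home at an approximate time, so missed or late doses add noise. The T3 window of ±5 days lets week 1 fall anywhere from day 2 to day 12, which affects both samples. The more basic defect may be that no difference is predicted without any margin.

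These points limit the concern without removing it. Listing the troughs attaches no criterion to them, and the one criterion that is written down uses the other sample. In the calculations above the trough was at least as sensitive wherever either sample could detect a rise, including with missed and mistimed doses. Adding a margin to the 45-minute comparison would still apply it to a diluted ratio.

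**Conclusion.** The point holds as one about the stated criterion. Objective 1 and Hypothesis 4 rest stabilisation on the less direct of two samples that are both already being drawn.

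The size is conditional. If the new dose makes up about 75% or more of the 45-minute level (k of 3 or above), a true 50% rise in trough would be missed in roughly half or more of trials like this one, while the trough comparison would detect it in at least 78%. Under slow one-compartment kinetics there is almost no loss.

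A reader might go further and infer that the 45-minute level is dominated by absorption, so that continuing accumulation would usually be missed. The documents do not support that. They give no time to peak, half-life or variability for this capsule, and the case of a 4-day slow half-life with a small slow phase is detected at 45 minutes in most simulated trials. They also give nothing that would justify assuming the favourable case. All the powers above rest on assumed kinetics and CVs; only the dilution formula does not need a particular kinetic model.

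**What to change.** In section 3.2 (objective 1) and Hypothesis 4, make the steady-state measure the within-participant log ratio of pre-dose CBD at T6 against T3, supported by T4 and T8. Report it as a geometric mean ratio with its 95% confidence interval, so that non-significance alone is not read as stability. State the same in section 20.3.3 and in the forthcoming SAP, naming the sample type for each comparison. Record the clock time of the last capsule before each draw, so that only true pre-dose samples enter. Keep the 45-minute comparison as a descriptive post-dose measure.

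The cost is the wording of one objective and one hypothesis, the matching analysis text, and one recorded time per visit. No blood draw is added, and dose and visit schedule are untouched. The downside is that a few samples with a mistimed or missed last dose drop out, which widens the interval somewhat.
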